### 11.4.3 Adverse Events

The overall observation period for AEs will be divided into 3 parts:

- Pre-treatment period: From the day of the patient’s informed consent to the day before the first dose of nivatrotamab
- On-treatment period: From the day of the first dose of nivatrotamab to 30 days after the last dose of nivatrotamab
- Post-treatment period: From 31 days after the last dose of nivatrotamab and thereafter

If dates are incomplete in a way that clear assignment to pre-, on-, post-treatment period cannot be made, the respective data will be assigned to the on-treatment period.

Additional analyses and presentations will be included in the SAP.

AEs will be presented descriptively in summary tables and listings.

AEs will be regarded as Treatment-emergent AEs (TEAEs) if they occur after the start of the first IMP administration.

A TEAE is defined as an AE that emerges during treatment having been absent pre-treatment (i.e., has onset on or after the first dose of study treatment).

AEs with onset during the pre- and post-treatment periods will be listed. AEs with onset during the on-treatment period will be summarized as follows:

- Summaries of AEs by MedDRA SOC and PT will be presented for all TEAEs, related TEAEs, CTCAE grade 3 or higher TEAEs, related CTCAE grade 3 or higher TEAEs, injection-related TEAEs, SAEs, related SAEs, CTCAE grade 3 or higher SAEs, related CTCAE grade 3 or higher SAEs, TEAEs leading to treatment discontinuation, and AEs leading to death.

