### **6.2.7 Screening/Pre-treatment Evaluation**

Pre-treatment evaluations should be completed within 21 days prior to the start of treatment (Day 1 of Cycle 1). Please refer to the screening (SCR) visit in the flowcharts for a summary of the procedures to be undertaken related to screening/pre-treatment evaluation in the trial (section 3).

Procedures to be performed only at screening:

- (i) Eligibility check (based on inclusion and exclusion criteria [see section 6.3.2]; the most recent imaging and laboratory assessment must be used to evaluate eligibility)
- (ii) Obtaining informed consent (written informed consent must be obtained from each patient within a reasonable time prior to the performance of any trial-related

procedure. Local recommendations regarding handling of informed consent will be followed)

(iii) Recording of medical history (including concomitant disease and smoking history) and data pertaining to demographic and baseline characteristics

Additionally, patients will undergo recording of information on concomitant medication and concurrent procedures, a physical examination (including a neurological examination [see section 8.1.3.1]), assessment of vital signs, height, body weight, Eastern Cooperative Oncology Group [ECOG] performance scoring,  $\beta$ -human chorionic gonadotropin [HCG] test (for pregnancy detection in females of childbearing potential), a 12-lead electrocardiogram (ECG), echocardiogram or multigated acquisition scan (MUGA), computed tomography (CT) scan of the primary tumor site, cranial and spinal magnetic resonance imaging (MRI) to evaluate CNS metastasis, clinical safety laboratory assessments (hematology, coagulation and clinical chemistry), assessment of SAEs, and urinalysis.

Any data that is generated within the screening period and is considered standard of care as per local procedures is permitted to be used for the evaluation of patient eligibility even if the evaluation is performed prior to signing of the informed consent form (see also section 8).

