### 9.5.1 Non-serious Adverse Events Reporting

Non-serious AEs (including non-serious AESIs) should be reported from signing informed consent until 30 days after the last IMP administration.

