### **9.6.2 Onset Date and Time**

Start date for an (S)AE is the date of occurrence of the first symptom. As a minimum, the time should be entered if the event starts on a dosing day of IMP or if the duration of the event is less than 24 h.

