### **9.6.5 Severity**

The Investigator will use CTCAE version 5.0 to describe the severity of the AE apart from AEs of CRS (see section [9.6.1.1](#)). If the severity changes over the course of the event, the grade assigned by the Investigator should be the most severe that occurred during the AE period. For grading of CRS and neurological AEs please see section [7.2.4](#).

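### An adverse event that starts between consent and first dose and worsens on nivatrotamab may appear only in a listing, because section 11.4.3 counts adverse events by onset alone

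*Combined protocol and SAP*

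**What the plan says.** Section 11.4.3 divides the observation time into a pre-treatment period (consent to the day before first dose), an on-treatment period (first dose to 30 days after last dose) and a post-treatment period. It describes a treatment-emergent AE (TEAE) twice. First, AEs qualify "if they occur after the start of the first IMP administration". Then: "A TEAE is defined as an AE that emerges during treatment having been absent pre-treatment", which the text explains as onset on or after the first dose.

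The reporting rules follow the same line. "AEs with onset during the pre- and post-treatment periods will be listed", whereas "AEs with onset during the on-treatment period will be summarized as follows". That second lead-in governs every table named after it, including the SAE tables and the table of AEs leading to death, which do not carry the TEAE label.

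Three other sections determine which events fall on which side:
- **Collection.** Non-serious AEs "should be reported from signing informed consent until 30 days after the last IMP administration" (9.5.1), and 9.5.2 sets the same period for SAEs. Section 6.2.7 sets the screening window: "Pre-treatment evaluations should be completed within 21 days prior to the start of treatment".
- **Dating.** "Start date for an (S)AE is the date of occurrence of the first symptom" (9.6.2).
- **Grading.** If severity changes, "the grade assigned by the Investigator should be the most severe that occurred during the AE period" (9.6.5).

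Incidence and severity of AEs is the phase 2 primary endpoint and one of the phase 1 primary endpoints (5.2.1).

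**The concern.** A definition of treatment emergence usually has two arms: new onset after dosing, and worsening after dosing of something already present. Section 11.4.3 has only the first. Because collection starts at consent, there is a window of up to about three weeks in which a new AE can start before any drug is given. If it then becomes grade 3 or serious on nivatrotamab, the change took place on treatment, but the tables look only at the start date.

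For these events the rule works in one direction: it can lower the tabulated incidence or severity but never raise it. The groups are small, so a single patient is visible in a row.

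**Working it through.** The plan gives no figure to reproduce. The check traces one case through the text and then works out the effect of one patient.

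**Test case.** A new grade 1 symptom, unrelated to the cancer, starts after consent and before first dose with a known date. It reaches grade 3 after dosing.

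1. It is reportable, because collection runs from consent (9.5.1, 9.5.2).
2. It is not a pre-existing condition under 9.1. That category covers disorders present before AE reporting began, that is, before consent, so its worsening clause does not apply.
3. When it worsens, its start date remains the first symptom (9.6.2) and its grade becomes the worst grade (9.6.5). An end date is entered only for fatal or recovered outcomes (9.6.3), and the outcome list has no term for worsening (9.6.6). Nothing tells the site to close one record and open another.
4. It fails the TEAE definition, because it was present before treatment and its onset is before first dose.
5. It fails the table lead-in for the same reason, so it is listed only.
6. The incomplete-date rule in 11.4.3 does not help. It moves an event to the on-treatment period only when the dates do not allow clear assignment.

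**What falls outside the gap.** The following are AEs in their own right when they change, and can have on-treatment onset:
- worsening of a condition present before consent (9.1);
- clinically significant worsening of a concomitant illness, including one found through screening (9.1 with 8.1.2);
- an unexpected change in the intensity or frequency of SCLC symptoms (9.6.4);
- a laboratory abnormality that first becomes clinically significant on drug (9.1).

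What remains is mainly new, symptomatic, non-SCLC events from the consent-to-dose window. Reactions to the injection itself cannot start before dosing.

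**Effect of one affected patient.** The group sizes are those used in section 11.2. If the patient has no other event in the same system organ class or preferred term row, the row percentage falls by 1/N:
- phase 2, N = 30: 1/30 = 3.3 points
- dose level of 9: 1/9 = 11.1 points
- dose level of 6: 1/6 = 16.7 points
- dose level of 3: 1/3 = 33.3 points

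An overall rate, such as any TEAE or any grade 3 or higher TEAE, falls only if the patient has no other qualifying event. The documents give no rate for such events, so the number of patients affected cannot be derived.

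**The case against.** **The one-record reading is not express.** For non-serious events, 9.6.2 and 9.6.5 point to a single record with an unchanged start date, but nothing forbids a new record at worsening. Section 9.9 asks for an updated report when an ongoing SAE or AESI changes in intensity, and says nothing comparable for other events. The eCRF completion instructions (referred to in 9.8) and the separate SAP (announced in 11.1) could settle the matter and are not among the documents. This stands. A reader might infer that every such event is certainly lost from the tables; the text supports only that it would be on the natural reading.

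**Safety decisions do not rest on these tables.** This also stands. In phase 1, DLTs are tabulated separately (11.4.1) and drive the MTD. The sponsor shares all SAEs with the DMC during phase 1 and until the phase 2 DMC meeting (9.9.3), and the stopping rules (6.2.5) are not tied to TEAE status. A reader might infer a risk to dose escalation or monitoring; the documents do not support that. The DLT table gives phase 2 no cover, however, because it rests on an analysis set limited to dose escalation (11.3.3).

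**The size could be overstated.** A reader might multiply an assumed event rate by the 69 patients of both phases, or attach exact confidence limits to the affected rows. Neither is supported. No rate is given, 69 is an enrolment ceiling (Appendix 1 expects 18 to 23 patients in the escalation), and the plan presents AEs descriptively, with exact intervals specified for response and disease-control rates (11.4.7.2).

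**There is no contradiction in the plan.** That is correct: the onset rule is explicit. The point is that an explicit rule for a primary endpoint omits a class of on-treatment change.

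**Conclusion.** The concern holds in a limited form. Section 11.4.3 defines TEAEs and opens its summary tables by onset alone. On the natural reading of 9.6.2 and 9.6.5, a new AE from the consent-to-dose window that worsens in grade or becomes serious on nivatrotamab is listed and not tabulated. No other section brings it back.

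This rests on two conditions: the site keeps one record with the first-symptom date, and the missing SAP and eCRF instructions do not say otherwise. The number of patients is unknown and probably small, given the short window and the exclusions above. The direction is known: under-reporting of a descriptive primary endpoint, with the per-row effect of a single patient as calculated. The event is still visible in a listing. This is a worthwhile correction because it is cheap and concerns a primary endpoint; it is not a threat to the conduct of the trial.

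**What to change.** 1. **Section 11.4.3, definition.** Define a TEAE as an AE with onset on or after first dose, or an AE with onset between consent and first dose that worsens in grade or becomes serious from first dose to 30 days after last dose.
2. **Section 11.4.3, lead-in to the tables.** Summarize AEs with onset, or with worsening in grade or seriousness, during the on-treatment period, at the on-treatment grade.
3. **Section 9.6.5, with a matching line in 9.6.2.** When a pre-dose AE worsens after dosing, require either a dated change of grade or seriousness, or a new record dated at the worsening. A single undated worst grade cannot show whether the worsening came before or after first dose.
4. **Optional, section 9.1.** State that the worsening of a pre-consent condition or concomitant illness, already an AE there, takes its onset at the date of worsening.

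The cost is two sentences in 11.4.3, one line each in 9.6.2 and 9.6.5 (and in 9.1 if wanted), and one eCRF completion instruction. The downside is slightly higher reported AE rates and a small data-entry burden.

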## 5 TRIAL OBJECTIVES AND ENDPOINTS

### 5.1 Trial Objectives

#### 5.1.1 Primary Objective

##### Phase 1

- To determine the MTD and the RP2D of nivatrotamab
- To assess the safety and tolerability of different doses of nivatrotamab

##### Phase 2

- To assess the long-term safety of nivatrotamab administered at the RP2D

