## 5.2 Endpoints

### 5.2.1 Primary Endpoints

##### Phase 1

- The MTD (defined by an mBOIN design) and the RP2D of nivatrotamab
- The overall incidence and severity of AEs for different doses of nivatrotamab

##### Phase 2

- Incidence and severity of AEs for nivatrotamab dosed at the RP2D

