## 6.2.13 Follow-up

### 6.2.13.1 Phase 1

All patients will be followed up for safety reporting for 30 days after the last IMP dosing. Thereafter, long-term safety will be recorded by registration of related SAEs up to 12 months after the last dose. The Investigator must commit to provide data on vital status and disease progression for follow up on PFS and OS up to 12 months after the last dose. In phase 1, ORR will be assessed at predefined timepoints, including at Week 24. The Investigator should collect CT scan reports for tumor assessments every 8 weeks or according to the local standard of care. The FU assessments can be done locally at the referral site.

### 6.2.13.2 Phase 2

Follow up in phase 2 will be similar to that in phase 1. All patients will be followed up for safety reporting for 30 days after the last IMP dosing. Moreover, long-term safety will be recorded by registration of related SAEs up to 12 months after the last dose. Vital status and disease progression for follow up on PFS and OS will be up to 12 months after the last dose. In phase 2, ORR will be assessed at pre-defined timepoints, including at Week 24. The Investigator should collect CT scan reports for tumor assessments every 8 weeks or according to the local standard of care. The FU assessments can be done locally at the referral site.

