## 6.2.14 End of Trial

End of trial is defined as last patient's last visit, follow-up contact or death in the long-term FU period.

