### 9.5.3 Adverse Events During Follow-Up

During the follow-up period, SAEs at least possibly related to nivatrotamab or to the study procedures and new onset of secondary malignancies regardless of causality, should be reported until end of the trial.

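### Phase 2's primary objective is long-term safety, but section 11.4.3 only lists events that start more than 30 days after the last dose, and its TEAE definition and the follow-up rules do not line up with its tables

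*Combined protocol and SAP*

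**What the plan says.** **Objective and endpoint.** Section 5.1.1 gives a single primary objective for phase 2: "To assess the long-term safety of nivatrotamab administered at the RP2D". The endpoint in section 5.2.1 is "Incidence and severity of AEs for nivatrotamab dosed at the RP2D", with no time window.

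**What is collected late.** Section 6.2.13 says that, beyond the 30-day safety period, "long-term safety will be recorded by registration of related SAEs up to 12 months after the last dose". Note d to Tables 3-1 and 3-2 agrees. Note k to the same tables and section 9.5.3 also require secondary malignancies whatever their cause. Section 9.5.3 says that these late events "should be reported until end of the trial". Section 6.2.14 defines that point for the trial as a whole, by the last patient's last visit, "follow-up contact or death in the long-term FU period".

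**What is analysed.** Section 11.4.3 sets the on-treatment period as "From the day of the first dose of nivatrotamab to 30 days after the last dose of nivatrotamab"; the post-treatment period starts on day 31. It then says "AEs with onset during the pre- and post-treatment periods will be listed" and restricts the SOC/PT summaries to on-treatment onset. Related SAEs and AEs leading to death are among the tables under that restriction. The same section says "AEs will be regarded as Treatment-emergent AEs (TEAEs) if they occur after the start of the first IMP administration", with no upper limit.

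**The concern.** The data that the protocol itself labels long-term safety are the data that the analysis section keeps out of its named tables. A related SAE or a secondary malignancy starting on day 40 after the last dose must be reported, but would count in no incidence figure specified for the primary objective. The phase 2 safety summary would then describe treatment plus 30 days under a long-term heading.

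Two inconsistencies add to this. The TEAE definition and the TEAE tables cover different periods, so a table titled as all TEAEs would not hold all events that meet the definition. And if late reporting runs to a trial-level date, the period after the last dose differs between patients, which matters as soon as anyone turns the listing into a rate.

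**Working it through.** **1. The plan's own figure.** The only quantity stated for phase 2 safety is the N=30 column of Table 11-1: the probability of at least one event, 1 − (1 − p)^30.

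| True rate p | Computed | Table 11-1 |
|---|---|---|
| 30% | 100.0% | 100% |
| 10% | 95.8% | 96% |
| 5% | 78.5% | 79% |
| 2% | 45.45% | 45% |
| 1% | 26.0% | 26% |
| 0.1% | 3.0% | 3% |

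The column reproduces. It carries no time window, and nothing in this point changes it or the sample size.

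**2. Follow one event through the text.** Take a related SAE starting 60 days after the last dose.
- Reported? Yes: section 6.2.13, note k and section 9.5.3 all require it.
- A TEAE by definition? Yes: its onset is after the first dose, and no end date is given.
- In the related-SAE or related-TEAE table? No: those tables need onset within 30 days of the last dose.
- In a listing? Yes.

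**3. How much observation time is listed only (12-month rule).** Inputs: 14-day cycles, at most 13 (section 6.2.1.1); dosing on Day 1 from Cycle 3 onward (section 8.1.5); last dose + 30 days (section 11.4.3); 12 months, taken as 365 days (section 6.2.13).

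Last dose in cycle k falls on day L = 14(k − 1) + 1. Listed-only days = 365 − 30 = 335. Total days = L + 365. Share = 335 / (L + 365).

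| Cycles | L | On-treatment days (L + 30) | Total days | Listed-only share |
|---|---|---|---|---|
| 13 | 169 | 199 | 534 | 63% |
| 6 | 71 | 101 | 436 | 77% |
| 4 | 43 | 73 | 408 | 82% |

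A coarser version in months, 11 / (T + 12), uses treatment lasting T = 1.4 or 3.5 months (median PFS figures in section 4.1) or 6.0 months (about the 26-week maximum). It gives 82%, 71% and 61%.

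**4. How far the two follow-up rules can diverge.** Assumptions: phase 2 recruits over 6 months (section 6.2.6, an estimate), and the last patient has 13 cycles plus 12 months. With 30.4375 days per month, the trial ends 6 × 30.4375 + 169 + 365 = 716.6 days after the first phase 2 patient starts. That first patient's time from last dose to end of trial is:
- 13 cycles: 716.6 − 169 = 547.6 days, 18.0 months;
- 4 cycles: 716.6 − 43 = 673.6 days, 22.1 months.

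Under section 6.2.13 it is 12 months in both cases.

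**The case against.** Several points on the other side are fair.

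- **The SAP may add a table.** Sections 11.1 and 11.4.3 leave further analyses to the SAP. A reader might infer that late events will certainly appear in no table at all; the text does not support that. It supports only that no such table is named. But a general deferral does not undo an explicit rule that these events are listed.
- **Listed is not lost.** With 30 phase 2 patients and only related SAEs and secondary malignancies collected late, the listing should be short. A late related death would be visible there and would count in OS (section 11.4.8), although OS does not attribute it to the drug.
- **The tables are not short-term only.** They cover up to 26 weeks plus 30 days, so longer-term safety is partly summarised. The gap is the post-treatment part.
- **A 12-month, patient-level reading of section 9.5.3 is plausible.** That section opens by referring to the follow-up period, which the synopsis sets at 12 months, and section 9.9 speaks elsewhere of a patient's own end of trial. The content of Figure 9-1, to which section 9.5 refers, is not available. A reader might infer that early patients will in fact be observed longer; no scheduled contact beyond 12 months is described, so this is not established.
- **The TEAE wording also refers to emergence during treatment.** It does, but the clarification attached to it mentions only onset on or after first dose. The tables' own restriction is clear; the definition does not match it.

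**Conclusion.** The point holds in this form: for a primary objective of long-term safety, section 11.4.3 names no summary of the late related SAEs and secondary malignancies that the protocol collects for that purpose. The TEAE definition and the late-reporting rules also need to be aligned. It should be corrected, but it affects reporting only; sample size and data collection stand.

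The 63% to 82% by day count (61% to 82% by the monthly version) is the share of calendar time for a patient who survives all 12 months after the last dose. It would be tempting to read it as the share of events or of risk that is missed. The documents do not support that: collection is narrower after day 30, and many patients will not live that long, given the median OS of 7.8 to 9.3 months and the 12-month OS of 34.2% cited in section 4.1 for other agents. Treatment durations are illustrative, and much of the dosing schedule is redacted. The 18 and 22 months apply only if section 9.5.3 is read at trial level and the recruitment estimate holds.

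**What to change.** 1. In section 11.4.3, add a separate descriptive table of post-treatment related SAEs (including fatal ones) and secondary malignancies, by SOC/PT and platinum stratum. Use the number of patients still under follow-up, or person-time, as denominator.
2. Keep this table apart from the on-treatment table of AEs leading to death. Section 9.6.4 requires deaths from any cause, including disease progression, to be reported as SAEs, whereas late collection under section 9.5.3 is limited to related SAEs and secondary malignancies. Merging the two would mix different kinds of event.
3. End the TEAE definition 30 days after the last dose, so that it matches the tables.
4. Reconcile the length and scope of late safety reporting across section 6.2.13, section 9.5.3 and notes d and k to Tables 3-1 and 3-2. If reporting is meant to continue beyond 12 months, keep it and restrict the new table to a common 12-month window, so that no reporting duty is shortened for the sake of the table.

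Cost: one extra table and a few wording changes, with no new visits or data. The downside is that the table will probably hold few events in about 30 patients, and should be read descriptively.

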Currently, the only approved first-line treatment approach for ED in SCLC is platinum-based chemotherapy with or without the addition of an immune checkpoint inhibitor, namely, atezolizumab or durvalumab. Platinum (cisplatin or carboplatin) remains the cornerstone for the treatment of SCLC of any stage, with high initial responses (including rapid responses and symptomatic improvement) reported in 70% to 80% of patients following first-line platinum- and immunotherapy-based treatment regimens; nevertheless, virtually all SCLC patients with ED develop tumor progression, mostly within 6 months.

Until recently, in the second-line setting, the topoisomerase I inhibitor, topotecan, was the only drug approved by the US Food and Drug Administration (FDA) and the European Medicines Agency (EMA). In randomized clinical trials, topotecan has been associated with overall response (OR) rates of 16.9% to 21.9%, median progression-free survival (PFS) of 3.4 to

3.5 months, and median OS of 7.8 to 8.7 months . Outcomes are particularly poor among patients with platinum-resistant disease, generally indicated by tumor progression within 90 days of completion of first-line therapy ; the OR rates in these patients are usually below 10% . In a typical clinical population, the response rate thus rarely exceeds 15%.

There is no globally approved therapeutic agent for patients with progressive SCLC following second-line treatment. However, for this patient population, FDA granted accelerated approvals to 2 compounds: nivolumab in August 2018 (based on the CheckMate 032 trial; ClinicalTrials.gov id: NCT01928394) and pembrolizumab in June 2019 (based on the Keynote trials 158 [NCT02628067] and 028 [NCT02054806]). Third-line treatment with checkpoint inhibitors are associated with benefit in a small percentage of patients, primarily in the platinum-sensitive subpopulation, with objective response rates (ORRs) ranging from 11% to 33% in clinical trials . Unfortunately, despite such response rates, most patients treated in these trials did not appear to benefit, as evidenced by median PFS of only 1.4 to 2 months. As a consequence to neither of the trials meeting the predefined endpoint of OS, the indication of checkpoint inhibitors in 3rd line for SCLC was subsequently withdrawn in December 2020 (nivolumab)  and March 2021(pembrolizumab) .

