Recently, FDA granted accelerated approval to the RNA polymerase II inhibitor, lurtinectedin, as monotherapy for patients with metastatic SCLC with disease progression during or after platinum-based chemotherapy . Efficacy of lurtinectedin was demonstrated in the PM1183-8B-005-14 trial (ClinicalTrials.gov id: NCT02454972), a multicenter open-label, multi-cohort (basket) trial enrolling 105 patients with metastatic SCLC. Among the 105 patients, the ORR was 30% with a median response duration of 5.1 months. The median PFS was 3.9 months and the 6-month PFS rate was 33.6%. In the subgroup of patients with platinum-resistant disease, the ORR was 22% (45% in platinum-sensitive patients), median PFS was 2.6 months, and the 6-month PFS rate was 18.8%. At a median follow-up of 17.1 months, the median OS with lurtinectedin was 9.3 months; the 12-month OS rate was 34.2%. The grade 3–4 adverse event (AE) frequency was 34% and events comprised mainly myelosuppression (hematological toxicities).

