## 11 STATISTICAL METHODS AND DETERMINATION OF SAMPLE SIZE

### 11.1 General Overview

The data will be summarized in tables, as appropriate, showing the number of patients with non-missing data (n), mean, standard deviation, median, minimum, and maximum for continuous data and counts and percentages for categorical data. Data will also be listed as deemed appropriate. All statistical analyses will be performed and data appendices created by using SASTM version 9.4 or later.

Any statistical tests will be 2-sided with an  $\alpha$  (significance) level of 0.05.

Data from patients who were screened but never started treatment will be listed. Screening failures will not be included in any of the analyses and summary tables.

The results will be presented by groups and total. In the dose escalation phase of the trial, groups will be defined by dose-levels, and in the dose expansion phase, groups will be defined by sensitivity/resistance to previous platinum therapy.

Patients in the dose escalation phase, for whom major inclusion/exclusion criteria and dose regimen are the same as for the patients in the dose expansion phase, may be included in the analyses and presentations of the dose expansion results.

For the sake of the statistical analyses and summaries, the baseline value is defined as the value collected at the time closest to, but prior to, the start of the first nivatrotamab administration. Measurements made on the same day as the first nivatrotamab administration are assumed to have been performed pre-treatment, unless recorded, or by this trial protocol stipulated, otherwise.

The statistical analysis plan (SAP) will describe in further detail the analyses presented below. Furthermore, handling and presentation of data, including demographics, baseline data, and other trial assessments, will be described in more detail in the SAP.

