### 11.2 Sample Size

Up to 39 patients may be included in the dose escalation phase. This number is based on the operational characteristics in [Appendix 1](#), including the up to 10 additional patients who may be added to any dose-level as described in section [6.2.1.4](#).

The impact of sample size on the detectability of AEs during dose escalation (when N=3, 6, or 9 patients at a dose level) and during dose expansion (when N=30) is shown in [Table 11-1](#).

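### Phase 2 long-term safety is summarised only as crude percentages of all dosed patients, with no allowance for time on treatment, and events after day 30 are only listed

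*Combined protocol and SAP*

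**What the plan says.** - **Objective and endpoint.** The only phase 2 primary objective in section 5.1.1 is "To assess the long-term safety of nivatrotamab administered at the RP2D". The endpoint in section 5.2.1 is "Incidence and severity of AEs for nivatrotamab dosed at the RP2D", with no time horizon.
- **Summary measure.** Section 11.1 specifies "counts and percentages for categorical data". Section 11.3.2 makes the safety set (all patients with at least one dose) the default for the primary objective. Section 11.1 presents phase 2 results in total and by platinum sensitivity.
- **Window.** Section 11.4.3 defines the on-treatment period as first dose to 30 days after the last dose. Its tables by SOC and PT cover that period only ("AEs with onset during the on-treatment period will be summarized as follows"); later events are listed.
- **Later collection.** Section 6.2.13.2 records long-term safety through related SAEs for up to 12 months after the last dose. Section 9.5.3 adds procedure-related SAEs, and secondary malignancies whatever their cause.
- **Exposure.** Treatment runs for up to 13 cycles of 14 days (26 weeks). Under section 6.3.3.1 it ends at confirmed or clinically judged progression; clinically stable patients may continue past unconfirmed progression.
- **Detectability.** Section 11.2 introduces Table 11-1 as "The impact of sample size on the detectability of AEs during dose escalation" and expansion, using N=30 for the latter.
- **Deferral.** Section 11.4.3 leaves additional AE analyses to the SAP without naming any.

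**The concern.** A patient observed for 6 weeks and one observed for 30 weeks each count once in the denominator. If patients stop at different times, the percentage with an AE depends on both the hazard and the length of exposure. For an objective framed as long-term safety, readers will want to know what happens to patients who stay on the drug, and the crude percentage does not tell them.

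The two platinum groups are shown side by side. If the resistant group progresses sooner, it could show a lower AE percentage simply because it was treated for less time.

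The protocol specifies Kaplan-Meier methods with censoring for PFS, DoR and OS. It gives the phase 2 primary endpoint no method for unequal follow-up. The data that section 6.2.13.2 treats as the long-term safety record enter no summary table.

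**Working it through.** **1. The plan's own figure.** Table 11-1 uses P(at least one) = 1 − (1 − p)^N. At N=30 and p = 30, 10, 5, 2, 1 and 0.1%, this gives 100.0, 95.8, 78.5, 45.45, 26.0 and 3.0%. The table shows 100, 96, 79, 45, 26 and 3%. All 24 cells reproduce.

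**2. Inputs for time on treatment.** None is given for nivatrotamab. As an assumption, I use the PFS that section 4.1 cites for other drugs:
- Lurbinectedin, all patients: "The median PFS was 3.9 months and the 6-month PFS rate was 33.6" per cent.
- Lurbinectedin, platinum-resistant: median 2.6 months.
- Third-line checkpoint inhibitors: "as evidenced by median PFS of only 1.4 to 2 months".

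Time on treatment T is taken as exponential with median m, so its rate is d = ln 2 / m. It is capped at 6 months, and 1 month is added for the 30-day tail. The longest window is therefore 7 months.

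**3. Crude percentage under a constant AE hazard.** Let the risk over the full 7 months be 30%, so h = −ln(0.70)/7 = 0.05095 per month. Observed time is min(T, 6) + 1, and

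crude = 1 − e^(−h) × [ d/(d+h) × (1 − e^(−6(d+h))) + e^(−6(d+h)) ].

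For m = 3.9: d = 0.1777 and d + h = 0.2287. The bracket is 0.777 × (1 − 0.254) + 0.254 = 0.834, so crude = 1 − 0.950 × 0.834 = 0.208.

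| Median m (months) | Crude % | Relative to 30% |
|---|---|---|
| 3.9 | 20.8 | −31% |
| 2.6 | 17.9 | −40% |
| 2.0 | 16.0 | −47% |
| 1.4 | 13.5 | −55% |

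**4. Group comparison.** With the same hazard, the percentage is 20.8 at the all-patient median and 17.9 at the resistant median. That gap of about 3 points comes from exposure alone.

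**5. Detectability of an AE that arises only near Week 24.** Week 24 is day 168. With the 30-day tail, a patient is under AE observation if still on treatment at day 138, which is 4.53 months. The fraction is f = 0.5^(4.53/m), and the probability of seeing an AE with 10% risk among those patients is 1 − (1 − 0.10 f)^30.

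| Median m (months) | f | Of 30 | P(at least one) |
|---|---|---|---|
| 3.9 | 0.447 | 13.4 | 75% |
| 2.6 | 0.299 | 9.0 | 60% |
| 2.0 | 0.208 | 6.2 | 47% |
| 1.4 | 0.106 | 3.2 | 27% |

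The 10% row of Table 11-1 gives 96%. Counting only patients still on treatment at Week 24 would give lower values (18% at m = 1.4), but that ignores the tail in which AEs are still collected.

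**6. Detectability of an AE that can occur at any time.** With a constant hazard and 10% risk over 7 months, the crude risks at the four medians are 6.8, 5.8, 5.1 and 4.3%. The probabilities of at least one event in 30 are 88, 83, 79 and 73%. For a 30% risk they are 98.7% to 99.9%. The large loss in step 5 is therefore specific to late-onset events.

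**The case against.** Several points on the other side stand and limit the conclusion.

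- **A reader might infer that AEs are not seen beyond 30 days after the last dose.** That is true only of non-serious AEs and unrelated SAEs other than secondary malignancies. Related SAEs and secondary malignancies are collected later; the gap is that they are listed and not summarised.
- **A reader might take it as fact that most patients stop early.** The protocol does not say so. The inference comes from other drugs, partly in third line, whereas phase 2 requires a prior response to platinum and allows treatment past unconfirmed progression. It is plausible, since every cited median PFS is below 6 months, but it remains an assumption. The resistant-disease figures also do not describe all 30 patients.
- **A reader might assume that neuropathy and cardiac events need months of exposure.** Nothing in the protocol supports this. Section 7.2.2.2 expects neuropathic pain on Day 1-2 after administration, and the on-treatment LVEF checks fall in Cycles 1 and 2.
- **A reader might conclude that Table 11-1 is wrong.** It is not. It takes a per-patient event probability as given, and 30 is then the right N. A shorter observation time lowers that probability.
- **The crude percentage is a legitimate estimand:** incidence while on treatment, with progression and death as competing events. It falls short only as an answer about sustained exposure.
- **Late estimates will be imprecise.** With zero events, the two-sided exact 95% upper limit is 31% with 10 at risk and 60% with 4.
- **The SAP may add analyses.** The statement in section 11.4.3 names no method, however, and no separate SAP text is included in the combined document. In an open-label trial, the estimator for a primary endpoint is better fixed before the data are seen.

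**Conclusion.** The point holds as a gap in the stated analysis. The phase 2 objective is long-term safety, but the specified summary does not separate AE risk from time on treatment, in total or by platinum group, and the later safety data enter no table.

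If time on treatment follows the cited PFS (exponential, medians 1.4 to 3.9 months), a constant-hazard AE with 30% risk over 7 months appears as 13.5% to 21%. An AE with 10% risk confined to about Week 24 is seen with probability 27% to 75%. For AEs that can occur throughout, the loss of detectability is modest (73% to 88% for a 10% risk). For AEs that occur early in every patient, Table 11-1 applies as it stands.

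The documents do not support saying without qualification that AE risk is understated; that depends on which risk is meant. No decision rule in the protocol is affected. What is at stake is how the phase 2 primary result is read, and the remedy is cheap enough that it should be made.

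**What to change.** In section 11.4.3, for phase 2 in total and by platinum group, keep the crude tables and add:

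1. A summary of time on treatment and person-time at risk.
2. Exposure-adjusted rates (first events per patient-month) for the main AE categories and AESIs.
3. Cumulative incidence at Weeks 4, 12 and 24 with numbers at risk, using first dose to 30 days after the last dose as the risk window and death as a competing event. State how progression-driven stopping is handled: as a competing event if the while-on-treatment risk is wanted; if it is censored, note that the censoring may be informative.
4. A summary table of related SAEs and secondary malignancies with onset more than 30 days after the last dose.

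In section 11.2, keep Table 11-1 and add a note that its N=30 column refers to the per-patient probability over the time actually observed. The note should say that far fewer patients would be under observation for an AE arising only near Week 24 (roughly 3 to 13 under the assumption above).

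The cost is SAP wording and one or two more tables from dates already collected, with no extra patients or visits. The late estimates will be imprecise, especially by platinum group, and should be labelled so.
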